8.3. Method of Treatment Assignment

Prior to dosing, subjects will be identified by their unique screening number assigned by the clinical site. On the morning of Day 1 and prior to receiving any apremilast, subjects who continue to be qualified for participation in the study will be enrolled and assigned a unique study number. All subjects enrolled in this protocol will receive apremilast.

8.4. Packaging and Labeling

The label(s) for apremilast will include Sponsor name, address and telephone number, the protocol number, apremilast name, dosage form and strength (where applicable), amount of apremilast per container, lot number, expiry date (where applicable), medication identification/kit number, dosing instructions, storage conditions, and required caution statements and/or regulatory statements as applicable. Additional information may be included on the label as applicable per local regulations.

8.5. Investigational Product Accountability and Disposal

The Investigator(s) or a qualified designee(s) is/are responsible for taking an inventory of each shipment of apremilast received, and comparing it with the accompanying apremilast accountability form. The Investigator(s) or qualified designee(s), will verify the accuracy of the information on the form, sign and date it, retain a copy in the study file, and return a copy to Celgene, where it will be maintained in the trial master file.

At the study site, all apremilast will be stored in a secure, locked area to prevent unauthorized access. Investigational product must be stored as directed on the bottle label(s).

The Investigator(s) or qualified designee(s) is responsible for the accountability of all apremilast issued to the site during the course of the study.

Celgene (or designee) will review with the Investigator and relevant site personnel the process for apremilast return, disposal, and/or destruction including responsibilities for the site versus Celgene (or designee).

8.6. Investigational Product Compliance

All doses administered in the clinic will be administered under direct supervision of trained staff. The individual(s) responsible for dosing will check the subject's mouth to ensure that the tablet has been swallowed whole (ie, not chewed or crushed).

The study staff will maintain an ongoing record of the dispensing and administration of apremilast for each subject via an accountability record or equivalent document that will be verified by Celgene's study monitor.

For apremilast dispensed to the subject/guardian for outpatient administration, study personnel will review the instructions printed on the package with the study subject and/or legal guardian prior to dispensing apremilast in tablet form. Investigational product will be dispensed as noted in the Table of Events, Section 5. The subjects will be instructed to return the apremilast containers, including any unused medication, to the study site at each visit for tablet counts and reconciliation. Subjects will be asked whether they have taken their apremilast as instructed at each study visit. Any problems with apremilast compliance will be reviewed with the subject. If a subject misses 4 or more consecutive days of dosing, Celgene should be contacted to decide whether dosing should resume or whether the subject should be terminated from the treatment phase of the study.

Gross compliance problems (eg, missing 4 or more consecutive days of dosing or taking less than 75% of the doses between study visits) should be discussed with Celgene.

Accurate recording of all apremilast administration (including dispensing and dosing) will be made in the appropriate section of the subject's eCRF and source documents.

CELGENE PROPRIETARY INFORMATION

9. CONCOMITANT MEDICATIONS AND PROCEDURES

9.1. Permitted Concomitant Medications and Procedures

Topical anesthetics will be permitted to prevent and control pain and discomfort associated with finger sticks during the DBS sample collection. Topical anesthetics (such as Eutectic Mixture of Local Anesthetics) should be administered as directed per the package insert. Prior to the blood collection procedure, fingers should be thoroughly wiped clean of the topical medication to avoid contamination of the PK blood sample.

Only inactivated vaccines will be allowed during the extension treatment phase.

Furthermore, subjects may take any medication that is not restricted by the protocol, is not expected to interfere with the conduct of the study and will not affect study assessments. Chronic medication should be dosed on a stable regimen and continued through the 2-week treatment phase.

All medications (prescription and non-prescription), treatments and therapies taken by the subject from Screening throughout the 50 weeks of treatment and the 4 and 8 week follow-up periods, including those initiated within 30 days prior to the start of the study, must be recorded on the subject's source document and on the appropriate page of the eCRF. The name of the medication/treatment, dose, unit, frequency, route, indication, the date the medication was started and the date the medication was stopped (if not ongoing) must be recorded. The recording of any permitted topical medications taken for psoriasis should also include the area of the body to which they are applied.

The following topical therapy will be permitted:

- Low-potency or weak corticosteroids (such as hydrocortisone, desonide, alclometasone dipropionate) will be allowed as background therapy for treatment of the face, axillae, and groin in accordance with the manufacturers' suggested usage during the course of the study.
- Subjects with scalp psoriasis will be permitted to use coal tar shampoo and/or salicylic acid soap preparations on scalp lesions
- An unmedicated skin moisturizer (eg, Eucerin[®]) will also be permitted for body lesions only

Subjects should not use these topical treatments within 24 hours to the clinic visit.

9.2. Prohibited Concomitant Medications and Procedures

The following psoriasis medications cannot be administered while subjects are receiving study medication.

- Topical therapy unless otherwise specified (including but not limited to topical corticosteroids, topical retinoid or vitamin D analog preparations, tacrolimus, pimecrolimus, or anthralin/dithranol: see Section 9.1)

- Systemic therapy including but not limited to cyclosporine, corticosteroids, methotrexate, oral retinoids, mycophenolate, thioguanine, hydroxyurea, sirolimus, sulfasalazine, azathioprine, and fumaric acid esters
- Phototherapy including UVB and PUVA
- Biologic agents such as etanercept, infliximab, adalimumab, certolizumab pegol, or ustekinumab
- Prolonged sun exposure or use of tanning booths or other ultraviolet light sources
- Use of an investigational drug

All vaccines will be withheld during the first 2 weeks of dosing. Live vaccines are not allowed at any time during active treatment with apremilast.

Subjects who need to be treated with protocol-prohibited medication will be withdrawn from the study.

9.3. Required Concomitant Medications and Procedures

Not applicable.

10. STATISTICAL ANALYSES

10.1. Overview

Descriptive statistics (mean, standard deviation [SD], median, minimum and maximum, and sample size) will be provided for quantitative data. Frequency tabulations will be compiled for classification of qualitative data. Graphical displays will be provided where useful to assist in the interpretation of results.

10.2. Study Population Definitions

Two study populations will be analyzed:

- Safety population: all enrolled subjects who take at least one dose of apremilast will be included in the safety population. Safety and efficacy analyses will be based on this population.
- Pharmacokinetic population: all enrolled subjects who take at least one dose of apremilast and have evaluable pharmacokinetic (PK) data will be included in the PK analysis. Pharmacokinetic data is considered evaluable if there are measurable drug levels of apremilast in plasma from at least 3 time points which extend over a minimal 5-hour period within 12 hours post a dose, eg, predose, 2 and 8 hours post a dose.

10.3. Sample Size and Power Considerations

No formal sample size calculation is performed. A sample size of at least 16 subjects per group has been selected to provide an adequate PK profile and safety assessment in subjects of different ages and body weight ranges. If needed, dropouts will be replaced to ensure that evaluable PK data from at least 32 subjects is collected.

10.4. Background and Demographic Characteristics

Subjects' age, height, and weight as baseline characteristics will be summarized using descriptive statistics. Gender, race and other categorical variables will be provided using frequency tabulations. Medical history data will be summarized using frequency tabulations by using the Medical Dictionary for Regulatory Activities (MedDRA) system organ class and preferred term classification system.

10.5. Subject Disposition

Subject disposition (analysis population allocation, entered, discontinued, along with primary reason for discontinuation) will be summarized using frequency and percent for both treatment and follow-up phases. A summary of subjects enrolled by site will be provided. Protocol deviations will be summarized using frequency tabulations.

10.6. Exploratory Efficacy Analysis

Exploratory efficacy endpoint(s) will be summarized using descriptive statistics.

10.7. Safety Analysis

Safety analyses will be performed for all subjects who received at least one dose of apremilast. Adverse events will be classified using MedDRA. Treatment-emergent AEs will be summarized by system organ class, preferred term, severity, and relationship to apremilast. Adverse events leading to death or to discontinuation from treatment and SAEs will be listed. In the by-subject analysis, a subject having the same event more than once will be counted only once and by greatest severity. Laboratory data will be summarized descriptively by visit (n, mean, median, SD, minimum, and maximum). Vital sign measurements, by visit, including weight, and concomitant medications and procedures, will be summarized descriptively. Data from the C-SSRS assessments and the stool diary will be summarized, respectively.

An independent DMC will review available safety and PK data at the following timepoints:

1. After the first 8 subjects in Group 1 have completed the 2 weeks of apremilast dosing, PK, and safety assessments.
2. After the first 8 subjects in Group 2 have completed the 2 weeks of apremilast dosing, PK, and safety assessments.

10.7.1. Internal Celgene Safety Monitoring During the Apremilast Program: Role of the Safety Management Team

In addition to daily safety monitoring conducted by investigators and individual study personnel, cumulative and interval AEs, serious adverse events (SAEs), discontinuations and laboratory findings will be reviewed internally by a Safety Management Team (SMT) at Celgene. The review follows the Council for International Organizations for Medical Sciences, Working Group VI recommendations. The SMT is comprised of lead representatives from multiple Celgene functions engaged in the apremilast development program. The scope, conduct, processes, and accountabilities of the SMT are specified in an SMT charter.

10.7.2. External Safety Monitoring During Apremilast Program: Role of the Independent Data Monitoring Committee

Monitoring will also be performed by an independent, external Data Monitoring Committee (DMC) that will assess safety as outlined in the DMC charter (available upon request). The DMC is comprised of three independent external trialists and an independent external statistician for whom there is no identified conflict of interest. The DMC will meet as outlined in Section 10.7 or ad hoc at the request of the SMT. The DMC scope, conduct, processes, and accountabilities are prespecified in its charter. Recommendations of the DMC based on the overall benefit/risk evaluation may include proceeding with the study per protocol, proceeding with the study with modification, or study suspension.

10.8. Pharmacokinetic Analysis

Pharmacokinetic parameters will be calculated using non-compartmental methods, plasma concentrations and actual blood sampling times from the intensive sampling schedule. Pharmacokinetic parameters and plasma concentrations for apremilast will be presented as descriptive statistics. The descriptive statistics will include but will not be limited to the following: sample size [N], mean, SD, coefficient of variation [CV%] geometric mean, and

geometric CV%. Results will be presented in tabular and graphic formats as appropriate. Population PK analyses will be performed using non-linear mixed effect modeling (NONMEM). Covariate analysis will be performed to identify relevant covariates. For all PK parameters, the population geometric mean will be estimated and provided. The between-subject variability will be reported as an apparent coefficient of variation (ie, square root of the estimated variance) if data permits. The following PK parameters will be determined:

- C_{\max}
- t_{\max}
- AUC_{0-12}
- AUC_{0-t}
- CL/F
- V_{ss}/F or V_z/F
- $t_{1/2}$

The following population PK parameters will be determined as appropriate:

- CL/F
- V/F
- K_a
- Lag (if applicable)

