4.2. Study Design Rationale

There is a paucity of treatments available for pediatric patients with moderate to severe psoriasis. Consequently, these subjects are treated off-label with the same systemic agents prescribed for adults. The currently available systemic therapies for psoriasis are associated with significant cumulative toxicities and are associated with risks of hepatic, renal and neurological toxicities that often require routine clinical and laboratory monitoring, as well as an increased risk of infections and malignancies. Given the chronic nature of psoriasis, there is a need for medication that can be dosed chronically with less risk. It is, therefore, important for new medications to demonstrate both efficacy and safety with continuous use. Apremilast provides a favorable

benefit/risk profile supporting the use of APR 30 BID in the treatment of adult patients with moderate to severe plaque psoriasis who are candidates for systemic and phototherapy.

Adolescents and children may differ from adults in their ADME of apremilast, hence evaluation of the safety and PK properties of apremilast in adolescents and children prior to initiation of an efficacy study in this subject population is warranted. Although apremilast has only been investigated in adult subjects, it is known that there is a general similarity of disease process, as reflected in PD parameters, between adult and pediatric populations. Assuming a similar exposure-response relationship in adults compared to adolescents and children, it is appropriate to initiate dosing in the pediatric population at a dose of 20 or 30 mg BID, depending on weight, that will provide overall drug exposure similar to that associated with the selected optimal adult dose.

In CC-10004-PSOR-008-PK, the concentration versus time profile of apremilast was well described by a population PK model.

A comparable exposure in pediatric subjects is expected to achieve a similar clinical response seen in psoriasis adult patients following 30 mg BID.

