7.2. Inclusion Criteria

Subjects must satisfy all of the following criteria to be enrolled in the study:

1. Male or female subjects 6 to 17 years of age, inclusive, at the time the informed consent document is signed by the legal guardian
2. **Group 1 Only:** ages 12 to 17 years, inclusive, and weighs ≥ 35 kg
3. **Group 2 Only:** ages 6 to 11 years, inclusive, and weighs ≥ 15 kg
4. Subject is able to swallow the apremilast tablet
5. Able to sign an assent with a legal guardian who can understand and voluntarily sign an informed consent
6. Able to adhere to the study visit schedule and other protocol requirements
7. Must agree to withhold vaccinations during the first 2 weeks of dosing. Inactivated vaccines will be allowed during the extension treatment period
8. Diagnosis of chronic plaque psoriasis for at least 6 months prior to Screening
9. Have moderate to severe plaque psoriasis at Screening and Baseline as defined by:
 - PASI score ≥ 12 ; and
 - Body surface area (BSA) $\geq 10\%$; and
 - sPGA ≥ 3 (moderate to severe)
10. Disease inadequately controlled by or inappropriate for topical therapy for psoriasis
11. Candidate for systemic or phototherapy
12. Have not been exposed to any or have been exposed to no more than one systemic agent for psoriasis
13. At Screening, laboratory values must be within the following ranges:
 - White blood cell (WBC) count

Age (yrs)	Males ($\times 10^3 / \mu\text{L}$)	Females ($\times 10^3 / \mu\text{L}$)
6-11	3.5 – 13.65	3.5 – 13.65
12-18	3.5 – 13.15	3.5 – 13.15

- Platelet count

Age (yrs)	Males (x 10 ³ /μL)	Females (x 10 ³ /μL)
6-11	117 – 394	117 - 394
12-18	126 – 400	126 - 400

- Serum creatinine ≤ 1.2 X upper limit of normal (ULN) for age and gender. Please see reference ranges of the central laboratory.
- AST (SGOT) and ALT (SGPT) ≤ 1.5 X ULN for age and gender. If initial test of ALT or AST is > 1.5 X ULN, one repeat test is allowed during screening. Please see reference ranges of the central laboratory.
- Total bilirubin ≤ 2 mg/dL (≤ 34 μmol/L). If initial test result is > 2 mg/dL, one repeat test is allowed during the screening period.
- Hemoglobin (Hb)

Age (yrs)	Males (g/dL)	Females (g/dL)
6-11	10.0 – 15.5	10.0 – 15.5
12-18	11.0 – 18.1	10.0 – 16.4

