10.9. Interim Analysis

No formal interim analysis is planned for this study. However, an extract of the PK and 2 weeks of safety data from the initial 8 adolescent subjects enrolled into Group 1 will be used to model the most appropriate dose for subsequently enrolled subjects (such that the exposure will be similar to the exposures in adult subjects administered apremilast 30 mg BID).

Pharmacokinetic data and 2-week safety data from at least 8 Group 1 subjects will be utilized to determine the appropriate dosage (dose strength/dose frequency) for subjects enrolled into Group 2.

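### Body weight is not prespecified in the population PK model, yet 8 adolescents of at least 35 kg inform dosing from 15 kg, and failing to find a weight effect in them is weak evidence that there is none

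*Protocol*

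**What the plan says.** Section 10.8 plans a NONMEM analysis of CL/F, V/F, Ka and lag. On covariates it says: "Covariate analysis will be performed to identify relevant covariates". It gives no weight term, exponent or reference weight.

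Section 10.9 says that data from "the initial 8 adolescent subjects enrolled into Group 1 will be used to model the most appropriate dose for subsequently enrolled subjects", with adult exposure on 30 mg BID as the target. It adds: "Pharmacokinetic data and 2-week safety data from at least 8 Group 1 subjects will be utilized to determine the appropriate dosage" for Group 2. Section 7.2 sets the weight floors: Group 1 is "ages 12 to 17 years, inclusive, and weighs ≥ 35 kg" and Group 2 is "ages 6 to 11 years, inclusive, and weighs ≥ 15 kg". Sections 4.1 and 4.2 start enrollment with older and heavier subjects.

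Three other places bear on this:
- Section 4.1 and the Protocol Summary give all Group 2 children one stated regimen if age and body weight turn out not to influence PK and safety. No criterion defines that finding.
- Section 1.3 says that initial regimens from 15 kg to below 70 kg should be adjusted for body weight.
- Section 4.2 refers to an adult model: "In CC-10004-PSOR-008-PK, the concentration versus time profile of apremilast was well described by a population PK model". Whether the pediatric analysis will use it is not stated.

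**The concern.** The step that opens Group 2 extrapolates from subjects of at least 35 kg to children who may weigh 15 kg. Weight is the variable on which the protocol bases its dosing, but the modelling text leaves its role open, and Section 4.1 attaches a consequence to finding no effect. In a sample of 8, an unimportant weight effect and an important but undetected one look much the same.

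If a non-finding is taken as no effect, the model assigns adolescent clearance to a small child. Predicted clearance is then too high and predicted exposure too low. Exposure similar to adults is the stated target, so the error falls on the quantity that the first review is meant to judge.

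**Working it through.** The plan states no power or precision (Section 10.3: no formal calculation), so there is no figure to reproduce.

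**Inputs from the protocol:** n = 8 at the first review; weight floors of 35 kg and 15 kg (Section 7.2); a second review with 8 + 8 subjects (Section 4.1).

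**Assumptions, not in the protocol:** true exponent b of weight on CL/F = 0.75 (0.25 to 1.0 also tried); CV of CL/F 30% to 50%; two-sided 5% test; weights of the 8 adolescents as listed below; the Section 10.8 search applied to the first 8 subjects.

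**1. Power with 8 adolescents.** The model is ln(CL/F) = a + b·ln(W). The residual SD is √ln(1 + CV²), which is 0.294, 0.385 and 0.472 for CV 30%, 40% and 50%. SE(b) = SD/√Sxx, where Sxx is the sum of squares of ln(W). Power comes from the noncentral t with 6 df (critical value 2.447).

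Example, weights spread evenly over 35–90 kg: Sxx = 0.751; at CV 30%, SE = 0.294/0.867 = 0.339, and 0.75/0.339 = 2.21 gives 46% power.

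| Weights of the 8 | Sxx | CV 30% | CV 40% | CV 50% |
|---|---|---|---|---|
| Even, 35–90 kg | 0.751 | 46% | 30% | 21% |
| Even, 35–70 kg | 0.408 | 28% | 18% | 14% |
| Even, 45–75 kg | 0.222 | 18% | 12% | 10% |
| Random, median 55 kg, log SD 0.22, cut to 35–90 kg | varies | 21% | 14% | 11% |
| Extreme: four at 35 kg, four at 90 kg | 1.784 | 81% | 59% | 43% |

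A likelihood-ratio test is more liberal: 60% to 28% for the 35–90 kg spread. The 95% half-width of b is 2.447 × SE, or 0.83 to 1.33 for 35–90 kg and 1.12 to 1.81 for 35–70 kg. Each exceeds the assumed effect of 0.75.

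**2. Error if weight is left out.** True/predicted AUC = (reference weight/W)^b, with reference weight 50 to 60 kg and b = 0.75:
- 15 kg: (50/15)^0.75 = 2.47 to (60/15)^0.75 = 2.83
- 20 kg: 1.99 to 2.28
- 25 kg: 1.68 to 1.93
- 30 kg: 1.47 to 1.68

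With b = 0.5 the ratio is 1.83 to 2.00 at 15 kg and 1.29 to 1.41 at 30 kg.

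**3. Chance of a more than two-fold error** (10,000 simulated sets of 8, random weights as above, CV 40%, true b = 0.75):

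| Rule | 15 kg | 20 kg | 25 kg | 30 kg |
|---|---|---|---|---|
| Keep weight only if p < 0.05 | 95% | 69% | 30% | 10% |
| Always estimate b from the 8 | 48% | 38% | 27% | 16% |
| Fix b = 0.75 | <0.1% | <0.1% | <0.1% | <0.1% |

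**4. If the fixed exponent is wrong.** The median true/predicted AUC at 15 kg is about (55/15)^(b − 0.75): 0.72 for b = 0.5, 1.38 for b = 1.0 and 0.52 for b = 0.25. The simulated chance of a more than two-fold error at 15 kg (CV 40%) is 0.4% for b = 0.5 or 1.0, but 39% for b = 0.25. With b = 0.25, keeping weight only if significant does better (6%).

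**5. Second review.** With 8 + 8 subjects (assumed 40–80 kg and 18–45 kg), Sxx = 2.868 and power is 98%, 87% and 71% at CV 30%, 40% and 50%. With all 32 it is above 99% to 95%.

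**The case against.** The strongest reply is that covariate parameterisation, fixed or estimated exponents and pooling with adult data commonly belong in an analysis or modelling plan, which is not at hand. Section 10.8 does not tie its search to the first 8 subjects, and Section 10.9 names no modelling method. Applying the one to the other is a reading. Text may also have been removed nearby: the weight paragraph in Section 1.3 opens without an antecedent, and the contents skip Section 1.5. All of this stands, and the missing exponent alone would not be a finding. What remains is in the protocol itself: a rule that acts on finding no weight effect, without a criterion, fed by 8 subjects of at least 35 kg and in tension with Section 1.3.

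A reader might infer more than the text supports:
- That weight enters only if the search retains it, or that the adult data will not be used. Both are read from silence.
- That 8 adolescents cannot show a weight effect. Power is low, but it reaches 81% with an extreme weight split at CV 30%.
- That a two-fold error applies from 15 to 30 kg. Leaving weight out gives 1.5 to 1.7 at 30 kg when b = 0.75.
- That the final pediatric dose selection is compromised. The data monitoring committee reviews PK before Group 2 opens and again after 8 Group 2 children. Data from both groups then guide the remaining regimens, and the first 8 children return if a regimen changes.

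The second review does not, however, protect those first 8 children during their initial two weeks.

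**Conclusion.** The point holds in a limited form. The protocol does not fix body weight in the model, extrapolates from 8 adolescents of at least 35 kg to children from 15 kg, and attaches a consequence to a no-effect finding that it does not define. Power to find an exponent of 0.75 is about 10% to 46% for plausible weight spreads. If weight is then omitted, exposure is under-predicted by a factor of about 2.0 to 2.8 at 15 to 20 kg and 1.5 to 1.7 at 30 kg. The exposed group is mainly the first 8 children in Group 2.

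The exponent, the CV and the weight spread are all assumptions. A shallower effect shrinks the error: with b = 0.25, omission gives (50/15)^0.25 = 1.35 to (60/15)^0.25 = 1.41 at 15 kg.

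**What to change.** In Sections 10.8 and 10.9, for the first review:
- Include body weight a priori on CL/F and V/F, allometrically (for example exponents 0.75 and 1).
- State whether the adult PSOR-008-PK data or model anchor the weight term.
- Run CL/F exponents from 0.25 to 1.0 as sensitivity. A range of 0.5 to 1.0 would miss the shallow case in step 4.
- Explore age, sex and other covariates on top, and re-estimate the weight exponent once Group 2 data exist.

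Show the data monitoring committee predicted AUC0-12 and Cmax over 15 to 70 kg, relative to adults on 30 mg BID, with a 90% interval. Define in Section 4.1 and the Protocol Summary what counts as no influence of age and weight, and state that a non-significant weight effect in 8 adolescents does not establish it. Reconcile the Protocol Summary and Sections 1.3, 4.1, 10.8 and 10.9. No dose or regimen is proposed here.

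The cost is wording and a modest amount of modelling, with no new data. The downside is that the starting exponent is an assumption, which the sensitivity run makes visible.
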